Study title: Effects of virtual reality on cardiorespiratory fitness test results

IRB approval number: 2130870

Document date: 6/7/2024

Statistical Analysis Plan

Analysis of data will be completed with SPSS version 29, applying an alpha level of .05. All data will be screened for data entry errors, outliers (difference scores >3.29 standard deviation units from the mean difference score between the two conditions), normality, and homogeneity of variance before formal analysis.

The primary outcome variables $\dot{V}O_{2\text{peak}}$ and workload at ventilatory threshold will be compared between conditions (Control and VR) using separate one-way repeated-measures ANCOVAs (analysis of covariance), with preference for exercise intensity subscale of the PRETIE-Q (Ekkekakis et al., 2005) as the covariate.

The secondary outcome measures of peak power, total test time, % $\dot{V}O_{2\text{peak}}$ at ventilatory threshold, heart rate (HR) at $\dot{V}O_{2\text{peak}}$, HR at ventilatory threshold, respiratory exchange ratio (RER) at $\dot{V}O_{2\text{peak}}$, and RER at ventilatory threshold will similarly be compared between conditions using a series of repeated-measures ANCOVAs with preference for exercise intensity subscale of the PRETIE-Q as the covariate.

Rating of perceived exertion (RPE) and affective valence will be analyzed with separate linear mixed-effects model analyses. Individual participants will be specified as the correlated random effect. The fixed factors will be timepoint and condition.

Results of ANCOVAs will be accompanied by partial eta squared (η^2) as a measure of effect size (small = 0.01; medium = 0.06; large = 0.14). Linear mixed-effect analysis results will use Cohen's d as a measure of effect size (small = 0.20; medium = 0.50; large = 0.80).

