Study title: Effects of virtual reality on cardiorespiratory fitness test results

IRB approval number: 2130870

Document date: 2/21/2024

Protocol Title:

Effects of virtual reality on cardiorespiratory fitness test results

Participants

A power analysis using G*Power version 3.1 will be conducted to determine sample size adequacy. We anticipate a moderate-large effect ($d = 0.7$) of VR on physiological outcomes based on past studies using similar designs (Rutkowski et al., 2021). With an alpha level of .05 and a power level of .80, an estimated 19 participants will be needed to observe a significant effect on $\dot{V}O_{2\text{peak}}$.

To account for participant dropout and missing data, we will recruit an additional 5 participants for a total of 24 participants. The primary means of participant recruitment will be the posting of approved informational flyers throughout the Forrest Hills, Summerville, and Health Science campuses of Augusta University. A secondary means of recruitment will be word-of-mouth. Approved study fliers will also be shared with other instructors at the affiliated institution so that they may announce the study opportunity to their students and share the flier on learning management systems.

Healthy men and (non-pregnant) women 18 years and older will be recruited to take part in this study. Prospective participants will be operationally defined as “healthy” according to results of the 7-item Physical Activity Readiness Questionnaire [PAR-Q; Warburton et al. (2019)]. Answering “yes” to any of the risk assessment questions will result in exclusion from study participation.

Research design

A repeated-measures crossover design will be used in which healthy participants complete a familiarization session and two experimental trials. Experimental days consisted of a maximal graded exercise test with (VR) and without (Control) the use of the immersive VR program separated by at least 1 week. The order of the conditions on the experimental trial days will be counterbalanced and randomized. Cardiometabolic data and psychological responses will be collected during the exercise tests to address the aims of the study. This study will be approved by the associated Institutional Review Board (project 2130870). Written informed consent for each participant will be obtained prior to their participation.

Instruments

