The participant will be fitted for the headgear that will be worn during maximal exercise tests on subsequent study visits. Plastic headgear is worn to keep the mouthpiece and gas collection hose in place during exercise so that expired air can be analyzed in the metabolic cart. The entire gas collection apparatus (headgear, mouthpiece, and gas collection hose) will be adjusted and worn for a brief warm-up on the exercise bike. The participant will pedal at a cadence of 50-90 rpm at a work rate of 50 Watts for 3 min. Work rate is adjusted and maintained at all times during exercise with the use of paired software installed on a computer adjacent to the exercise bike (CompuTrainer Inc., Seattle, WA). Responses to the CR-10 RPE and Feeling scales will be solicited at the end of minutes 1 and 3, to which participants will respond with designated hand gestures indicating the appropriate response. This process will be intended to increase the participants' familiarity with the exercise and gas collection equipment, reduce setup complications on future visits, and practice non-verbal communication of psychological scale responses.

An additional exercise stage of 3 min will follow this familiarization warm-up, during which the VR headset will be added to the gas collection apparatus. The participant will be walked through how to start the accompanying VR application and pedal for the designated time to ensure proper fit and function of all pieces of equipment simultaneously. Once this familiarization session is complete, the next visit to the lab will be scheduled and the participant will be directed from the lab.

Visits 2 and 3 – Experimental sessions

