The procedures for the two experimental session visits will be the same, aside from the use of the VR equipment in one of the visits. The order of the visits (control and VR) will be counterbalanced and randomized prior to the study commencement. Upon arrival to the lab, participants verbally confirmed that they had abstained from alcohol and strenuous exercise for the previous 24 hours and attained at least 6 hours of sleep the night prior to the visit. They will don the HR monitor, review the psychological scales, and adjust the exercise bike as needed. The gas collection apparatus will be donned and the collection tube will be connected from the mouthpiece to a metabolic cart that has been previously calibrated to the manufacturer specifications. The participant will sit on the exercise bike seat and, once ready, pedal against no resistance for 3 minutes as a warm-up. The exercise test will begin after the warm-up by increasing the resistance to 50 W and increasing the work rate by 25 W each minute thereafter until the termination of the exercise test (Bird et al., 2019). RPE and affective valence responses will be collected at the end of every odd numbered minute (end of minutes 1, 3, 5, etc.). Heart rate will be collected continuously and monitored throughout the test. See Figure 1 for visual timeline of data collection.

The test will be terminated upon volitional exhaustion (when the participant feels that they can no longer continue), when the participant fails to maintain cadence > 50 rpm for longer than 10 s, or when a plateau in $\dot{V}O_2$ (<100 ml/min increase with an increase in work rate) is observed (Poole, Wilkerson, & Jones, 2008). A cool-down period of 3 min at 0 W (no resistance) will immediately follow the termination of the exercise test. At the end of the cool-down, participants will complete the remembered pleasure scale. This will mark the end of the visit and the participant will be directed from the lab.

The experimental session visit which for which the VR equipment is used will be identical in all ways to the control condition, with the exception that the VR headset will be worn in addition to the other previously mentioned equipment. A video displaying natural scenery from the viewpoint of a cyclist will be viewed by the participant throughout the exercise test. Once both experimental visits have concluded, the participants' participation in the study is complete.

Figure 1. Data collection timeline during exercise tests

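### Visit order is randomised but no model in the SAP includes sequence or visit, so any change between the two maximal tests goes into the error term

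*SAP*

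**What the plan says.** The Protocol (Research design) sets out a crossover with one familiarisation visit and two test visits at least a week apart: "The order of the conditions on the experimental trial days will be counterbalanced and randomized". The section on Visits 2 and 3 adds that this is done before the study begins: "The order of the visits (control and VR) will be counterbalanced and randomized prior to the study commencement". Under Participants, 19 people are needed for the assumed effect, and the allowance for losses is: "To account for participant dropout and missing data, we will recruit an additional 5 participants for a total of 24 participants".

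The SAP lists all its model terms in three short paragraphs. For the primary outcomes, peak oxygen uptake and "workload at ventilatory threshold will be compared between conditions (Control and VR) using separate one-way repeated-measures ANCOVAs", the only other term is the PRETIE-Q preference score. The cardiorespiratory and performance secondary outcomes use the same model. For perceived exertion and affective valence, with participant as random effect: "The fixed factors will be timepoint and condition".

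Neither document names sequence, period, visit or order as a term in any model.

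**The concern.** In a two-period crossover, each participant's VR-minus-control difference contains the condition effect plus or minus any change from the first test to the second. The sign depends on which condition came first. A model without sequence treats that systematic spread as random error.

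Nothing else in the models can absorb it. The preference score is collected once, at Visit 1, so it does not record visit order. Timepoint matches the odd-minute readings within a test (Visits 2 and 3, and Figure 1), not the visit.

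Some change is plausible. Familiarisation rehearses the equipment only at low effort: "The participant will pedal at a cadence of 50-90 rpm at a work rate of 50 Watts for 3 min", then a further 3-minute stage with the headset. Visit 2 is therefore the first maximal test in the study, and one way that test can end is the participant's own decision to stop.

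At stake is precision. If the two orders finish in unequal numbers, the VR estimate is also shifted.

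**Working it through.** **Inputs.** From the Protocol: d = 0.7, alpha .05, power .80, 19 required, 24 recruited. Assumed: a 12/12 start (the exact split is not stated), two-sided testing, and p, the first-to-second-test change in SDs of the within-person difference. The documents give no value for p, so a range of 0 to .75 is shown.

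**1. The plan's own figure.** A two-sided paired t-test with d = 0.7 has power .799 at n = 18 and .823 at n = 19, so 19 reproduces. (One-sided would give 15.) At n = 24 power is .907. This calculation contains no period variance.

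**2. Model.** Let D = VR − Control, with residual SD 1:
- Control first: D = .7 + p + e
- VR first: D = .7 − p + e

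Without sequence, the estimate is shifted by p(n₁ − n₂)/n, where n₁ is the number completing Control-first and n₂ VR-first. The expected residual variance becomes 1 + p² × 4n₁n₂/[n(n − 1)].

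**3. Equal orders, 12/12.** The shift is zero. The variance factor is 4 × 144/(24 × 23) = 1.043. At p = .5, √(1 + .25 × 1.043) = 1.123. The true standard error of the mean has not changed, so the interval is 12% too wide and the test is conservative. Power and alpha come from simulation (200,000 replicates per cell). D was regressed on intercept and covariate, with and without sequence; the covariate was mean-centred and unrelated to D.

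| p | Excess CI width without sequence | True alpha without | Power without | Power with |
|---|---|---|---|---|
| 0 | 0% | .049 | .91 | .91 |
| .25 | 3% | .044 | .89 | .90 |
| .5 | 12% | .029 | .86 | .90 |
| .75 | 26% | .015 | .78 | .90 |

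**4. Nineteen completers.** If 5 of 24 are lost regardless of order, there are C(24,5) = 42,504 equally likely sets of losses:
- 10/9: 2 × C(12,2) × C(12,3) = 29,040, or 68%
- 11/8: 2 × 12 × C(12,4) = 11,880, or 28%
- 12/7: 2 × C(12,5) = 1,584, or 4%

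Results at p = .5:

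| Split | Shift in SD | Power without, more Control-first | Power without, more VR-first | Power with |
|---|---|---|---|---|
| 10/9 | .5 × 1/19 = .026 | .78 | .71 | .82 |
| 11/8 | .5 × 3/19 = .079 | .84 | .64 | .81 |
| 12/7 | .5 × 5/19 = .132 | .89 | .56 | .79 |

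Where power without sequence is the higher of the two, the reason is an estimate biased upwards. At 12/7 the expected estimate is .7 + .132 = .83, and at 7/12 it is .7 − .132 = .57. With sequence it is .70 in both cases. The highest type I error found was about .056, at the 12/7 split.

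**5. Averaged over these splits and both directions**, power without versus with sequence:
- p = 0: .82 versus .81
- p = .25: .80 versus .81
- p = .5: .74 versus .81
- p = .75: .65 versus .81

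**6. Analytic check.** The sequence model without the covariate has standard error ½√(1/n₁ + 1/n₂) on n − 2 df. The noncentral t gives power .906 (12/12), .819 (10/9), .810 (11/8) and .792 (12/7), in line with the simulation.

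**The case against.** The strongest reply is that the design already deals with order. It is randomised and counterbalanced, Visit 1 rehearses all the equipment, the tests are at least a week apart, and alcohol, exercise and sleep are checked beforehand. On this view p is probably small. At p = .25 the repair gains about .01 in power, and averaged over the 19-completer splits it breaks even only near p = .15. Validity is not at risk: with equal orders the test is conservative, and bias needs both a period change and unequal completion, and averages to zero when dropout is unrelated to order. Nineteen is also the case where the whole dropout allowance is used. With all 24 completing at 12/12, power at p = .5 is still .86, above target.

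There is a narrower point too. Stopping at will bears on peak oxygen uptake, peak power and test time. It bears less on workload, heart rate or RER at ventilatory threshold, which are normally reached earlier. Tests can also end on an oxygen plateau or on cadence failure.

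Most of this stands as a limit on size. It does not answer the omission. Counterbalancing protects the mean, not the residual variance, and it protects the mean only when completion is equal. The documents offer no specific reason for a period change in the threshold outcomes, but a term that costs one degree of freedom does not need one.

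**Conclusion.** The concern holds. The trial randomises order, and no model analyses by it. If there is no change between tests, nothing is lost. If there is one, the main expected cost is precision: a 3% wider interval at p = .25 and 12% at p = .5 with 12 per order. At 19 completers and p = .5, average power is .74 rather than .81, which falls below the planned .80. A material shift in the estimate needs lopsided completion; at 10/9, the most likely split, it is 5% of p.

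The figures rest on an assumed p, a 12/12 start, losses unrelated to order, and a mean-centred covariate unrelated to the difference. Leaving the covariate out changes power by at most about .006. The documents set no limit on p; the .75 row is a larger change than the planned VR effect itself. The mixed models share the omission, but the loss there was not sized. This is a precision repair that should be made, not a failure of validity.

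**What to change.** - **Every repeated-measures ANCOVA:** add randomised sequence (Control-first or VR-first) as a two-level between-subject factor. The condition-by-sequence term then carries the period effect. Report condition as the equally weighted average over the two sequences, and keep the term whatever its p-value. State that the preference score is mean-centred, as the figures here assume.
- **Exertion and affect mixed models:** add visit (2 or 3) as a fixed effect.
- **Reporting:** give the number of completers in each sequence.

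The change is to SAP wording only, because order is assigned before the study starts. It is best made before results are seen by condition, so that the term is not a later choice. The cost is one residual degree of freedom. With no period effect, power goes from .907 to .905 at 12/12, .820 to .816 at 10/9, .819 to .806 at 11/8, and .819 to .786 at 12/7. Averaged over the 19-completer splits, that is about .01.

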A stadiometer and scale (Continental Scale Corp., Bridgeview, IL, USA) were used to measure height and weight of participants. Body composition will be assessed using the InBody 570 bioelectrical impedance analysis device (InBody Co., Ltd, Seoul, South Korea). Participants removed socks and shoes before stepping onto the device. Body composition analysis will be performed according to manufacturer specifications. HR will be measured using a Polar H10 monitor (PolarElectro, Kempele, Finland), a valid and reliable instrument for measuring HR with strong agreement with the electrocardiogram (Schaffarczyk et al., 2022). The H10 monitor is worn on an adjustable belt secured at the xiphoid process over the skin as specified by the manufacturer.

All exercise will be completed on a Velotron cycle ergometer (SRAM, Chicago, IL) which will be paired with software for the investigator to control the intensity (CompuTrainer Inc., Seattle, WA). Expired gases were analyzed in a metabolic cart calibrated on the day of testing to manufacturer specifications (Parvo Medics TrueOne 2400, Marry, UT) via gas collection apparatus (Hans Rudolph Inc., Shawnee, KS). The Meta Quest 2 virtual reality headset (Meta Platforms, Inc., Menlo Park, CA, USA) will be used to run and display the virtual reality video during the VR condition GXT. The video will be a clip from www.YouTube.com which will be

modified using video editing software Adobe Premiere Pro (Adobe Inc., San Jose, CA) to increase speed at each stage of the exercise test to align optical flow with work rate. The Preferences for and Tolerance of the Intensity of exercise Questionnaire (PRETIE-Q) (Ekkekakis, Hall, & Petruzzello, 2005; Santos & Teixeira, 2023) will be used to assess individual preference for different exercise intensities, information which will be used as a covariate when analyzing maximal exercise test outcomes (Hutchinson et al., 2018). Participants completed the questionnaire digitally via the program Qualtrics on a laboratory computer or personal cell phone.

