Ratings of perceived exertion (RPE) were collected using the category-ratio 10-point scale. Affective valence will be assessed with the Feeling Scale. Both of these scales were delivered visually on the VR field of view when measurements were to be taken so that participants would be able to see the scale and associated verbal anchors. Remembered pleasure will be assessed using a visual analog scale after each exercise test has been completed and the VR headset has been removed.

Subsequent analysis of the metabolic data to identify $\dot{V}O_{2\text{peak}}$ and ventilatory threshold will be completed using the software WinBreak, version 3.1.

Procedures

Visit 1 - Familiarization

During the initial visit to the laboratory, participants will complete the PAR-Q survey, sign the informed consent if eligibility criteria were met, and then complete the PRETIE-Q. Height, weight, and body composition will be measured and recorded. Instructions for the CR-10 RPE scale and the feeling scale will be explained in detail and understanding will be verified by the investigator.

Once the HR monitor has been donned and it is verified to be working properly, the cycle ergometer will be adjusted to the comfort and preference of the participant. The seat height and handlebar positions will be adjusted until optimized for cycling exercise and the positions will be recorded for the participant's future visits.

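### The SAP does not fix the preference score at which the VR effect is tested; entered uncentred in a standard repeated-measures ANCOVA, the primary test is of the effect at score zero

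*SAP*

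**What the plan says.** The SAP analyses the two primary outcomes, VO2peak and workload at ventilatory threshold, in SPSS 29 at alpha .05 "using separate one-way repeated-measures ANCOVAs (analysis of covariance), with preference for exercise intensity subscale of the PRETIE-Q" as the covariate. Seven secondary outcomes are "compared between conditions using a series of repeated-measures ANCOVAs with preference for exercise intensity subscale of the PRETIE-Q as the covariate", so nine analyses share the specification. Effect sizes come from the same models: "Results of ANCOVAs will be accompanied by partial eta squared".

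The protocol (Instruments) says of the questionnaire only that it supplies "information which will be used as a covariate when analyzing maximal exercise test outcomes". Under Visit 1 - Familiarization, participants "sign the informed consent if eligibility criteria were met, and then complete the PRETIE-Q". No repeat is planned at Visits 2 and 3, so each person has one score, common to both conditions.

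Neither document says whether the score is centred, whether a condition-by-preference term is included, or at which score the condition effect is evaluated. Mixed models are named only for the ratings: RPE and "affective valence will be analyzed with separate linear mixed-effects model analyses".

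The sample size (protocol, Participants) mentions no covariate: at d = 0.7, alpha .05 and power .80, "an estimated 19 participants will be needed to observe a significant effect".

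**The concern.** A covariate measured once per participant cannot explain differences between that participant's own two tests unless it interacts with condition. What it does to the condition test therefore depends on the details the SAP leaves open. Without an interaction, the covariate drops out of the within-participant contrast. With an interaction, the condition term is the VR effect at the point where the covariate equals zero, and for an uncentred score that point is a preference score of zero.

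The intended target appears to be the average VR effect. The SAP compares the conditions as such, its outlier screen is built on the mean difference ("difference scores >3.29 standard deviation units from the mean difference score between the two conditions"), and the sample size is that of a paired comparison.

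Two analysts following the SAP could therefore obtain different primary p-values and effect sizes from the same data. On one permissible route, the reported F and partial eta squared would describe the wrong quantity.

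**Working it through.** **Inputs.** From the protocol: d = 0.7 (read as the mean paired difference over the SD of the differences), alpha .05 (taken as two-sided), power .80, N = 19, recruitment target 24. From the SAP: the model and the partial eta squared cut-offs (0.01, 0.06, 0.14). Not in the documents, so assumed: k, the mean of the preference score divided by its SD, varied from 0 to 6; and, for the last step only, r, the correlation between preference and the VR minus Control difference.

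**1. The plan's own figure.** A two-sided paired t-test has noncentrality 0.7√n on n − 1 df. Power is 0.799 at n = 18, 0.823 at n = 19 and 0.907 at n = 24. The stated 19 reproduces.

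**2. What the condition F tests.** Let D be VR minus Control and x the preference score. With two conditions and the interaction fitted, the within-participant part of the ANCOVA is D = a + b·x + error on n − 2 df, and the condition test is the test of a.

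- Score as collected: a is the VR effect at x = 0, with variance s²(1/n + x̄²/Sxx).
- Score centred: a is the mean difference, with variance s²/n.
- Ratio of the two variances: 1 + n·k²/(n − 1).

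Two simulated datasets with n = 19 confirm the identity:

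| Model | Dataset 1, condition t | Dataset 2, condition t |
|---|---|---|
| Interaction, score uncentred | 1.379 | 1.424 |
| Interaction, score centred | 1.990 | 2.570 |
| No interaction (equals the paired t) | 1.994 | 2.599 |

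In each dataset the first row equals the intercept t of the regression of D on x. In dataset 2 the choice of model moves the result across the 5% critical value (2.11 on 17 df).

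**3. Power when the VR effect is 0.7 SD at every preference score.** The noncentrality is 0.7√n / √(1 + n·k²/(n − 1)) on n − 2 df. For n = 19 and k = 3, the variance ratio is 1 + 19·9/18 = 10.5, and the noncentrality falls from 0.7√19 = 3.05 to 3.05/√10.5 = 0.94.

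| k | Power, n = 19 | Power, n = 24 |
|---|---|---|
| centred | 0.820 | 0.906 |
| 0.5 | 0.73 | 0.83 |
| 1 | 0.519 | 0.631 |
| 2 | 0.243 | 0.303 |
| 3 | 0.144 | 0.175 |
| 5 | 0.085 | 0.097 |
| 6 | 0.075 | 0.083 |

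Simulation agrees to within 0.002 at k = 2 to 6. Power drops below 80% once k exceeds 0.22 (n = 19) or 0.59 (n = 24), and below 50% once k exceeds 1.05 or 1.31.

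**4. Effect size.** Partial eta squared for this test is t²/(t² + n − 2). By simulation at n = 19, its median falls from 0.36 when centred to 0.10 (k = 2), 0.058 (k = 3) and 0.037 (k = 5). On the SAP's cut-offs that is a move from large to medium, then to just under medium, then to small.

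**5. False rejection when the average effect is zero but preference modifies it.** Simulated rejection rates at nominal 5%, for k = 3 to 5:

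| r | Uncentred, n = 19 | Uncentred, n = 24 | Centred |
|---|---|---|---|
| 0.1 | about 7% | about 7% | about 5% |
| 0.2 | 12–13% | 15% | 5–6% |
| 0.3 | 22–24% | 28–30% | about 6% |

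**The case against.** The strongest reply is that this is an omission, not a demonstrated error. The harm needs two choices together, an uncentred score and an interaction term, and the SAP makes neither. An analyst who reads ANCOVA as a common-slope model gets exactly the paired t-test, and one who centres the score complies fully with the SAP. In both cases 19 participants give 82% power. That the standard form carries the interaction is general methods knowledge, not document text. The low power figures rest on an assumed k; at k = 0.5 and n = 24, power is still 83%. The false-rejection figures need a further assumption, that preference modifies the VR effect, and at r = 0.1 the excess is small. An outlier rule is also only indirect evidence of the intended target.

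All of that is correct as to conditionality, and the power figures should be read as the performance of one permissible route, not as the expected performance of the trial. It does not remove the point. A SAP should determine the primary p-value before the data are seen. This one does not, and running the named model in its standard form on the raw score tests a quantity that nobody appears to want. The 80% crossing points are low, so substantial loss does not need an extreme k.

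**Conclusion.** The concern holds. The primary test is under-specified in the SAP. If the preference score is entered as collected and the condition-by-preference term is fitted, the condition F is exactly a test of the VR effect at a preference score of zero; this is algebra and does not depend on k.

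The size does depend on k, which the documents do not supply. Over k = 2 to 6, power for the planned effect is 24% down to 7.5% at 19 participants and 30% down to 8.3% at 24, against 82% and 91% when centred. The inflated false rejection applies only if preference also modifies the VR effect.

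The sample size is not in error: 19 is right for the paired comparison and stays adequate once the score is centred. This should be fixed before analysis because it leaves the primary result open. It is not proof that the wrong analysis will be run.

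**What to change.** Add to the SAP, for all nine repeated-measures ANCOVAs:

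- The preference score is centred at the mean of the participants included in that analysis. If outlier exclusions differ between outcomes, centre again for each analysed set.
- The condition effect is the mean VR minus Control difference at the average preference score, reported with a 95% CI, and partial eta squared is taken from that same test.
- The preference-by-condition term is fitted and reported separately, as effect modification.

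Making the paired comparison primary, with preference as an exploratory moderator, would also work, but it changes more of the plan than is necessary.

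The cost is one short SAP addition and a computed variable in SPSS. One error degree of freedom is used: power is 82.0% against 82.3% for the paired t-test at 19 participants, and 90.6% against 90.7% at 24. Recruitment and study procedures do not change.
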